***Likely to be Successful Group definition:**

- Completed all required study visits, AND ...
- Investigator would recommend the study CLs, AND ...
- The subjects' response on the MRD "overall quality of vision" and "overall comfort" questions as good, very good or excellent.

Likely to be Unsuccessful Group definition:

- Not meeting the definition of successful.

2.3. Hypotheses

Primary Hypothesis

- At least 75% of the subjects who are classified by Quest questionnaire as being "discontented and driven" will be in the "likely to be successful" group. The Quest questionnaire will be collected at baseline.

Secondary Hypothesis

- At least one of the secondary endpoints will be significantly correlated with the success classification of the subjects after adjusting for age, sex and ADD power.

3. TARGETED STUDY POPULATION

3.1. General Characteristics

There are no sex or race requirements for potential study Subjects.

All Subjects need to be in the presbyopic age group i.e. 40 years or older and with a minimum add of +0.75 D. All eligible Subjects will have no experience with soft multifocal lenses (MF CLs) for >2 years. The study population includes previous MF CL wearers, Single vision CL wearers and Subjects who are neophyte to CL wear. Current MF CL wearers and current monovision wearers are not eligible.

The study will include myopes only, with reading ADDs from +0.75 up to and including +1.75 DS.

3.2. Inclusion Criteria

Potential Subjects must satisfy all of the following criteria to be enrolled in the study:

1. The participant must read, understand, and sign the STATEMENT OF INFORMED CONSENT and receive a fully executed copy of the form.
2. Appear able and willing to adhere to the instructions set forth in this clinical protocol.
3. Is at least 40 years of age (inclusive) at the time of screening and has full legal capacity to volunteer.
4. Had a self-reported eye examination in the last two years.
5. The subject must either already be wearing a presbyopic correction (e.g., reading spectacles over contact lenses, or multifocal spectacles, etc.) or respond positively to at least one symptom on the "Presbyopic Symptoms Questionnaire".

6. Can achieve best corrected distance monocular visual acuity of at least +0.20 logMAR and binocular visual acuity of at least +0.10 logMAR with refraction.
7. Have a refractive cylinder of ≤ 1.00 D in each eye.
8. Has corrected best sphere equivalent distance refraction in the range -0.50 D of -6.00 D in each eye (vertex corrected if greater than -4.00D).
9. Have a reading ADD power in the range of +0.75 D to +1.75 D (inclusive) in each eye.
10. Have a wearable pair of spectacles (at the discretion of the investigator) to wear when they cannot wear the study lenses.

3.3. Exclusion Criteria

Potential Subjects who meet any of the following criteria will be excluded from participating in the study:

1. Participation in any contact lens or lens care clinical trial within 1 week prior to study enrollment.
2. Employee or immediate family member of an employee of the Centre for Ocular Research & Education listed on the study Delegation Log (e.g., Investigator, Coordinator, Technician).
3. Is currently pregnant or lactating, by self-report, or planning a pregnancy at the time of enrollment.
4. Has any known active ocular disease and/or allergies, ocular infections or other abnormalities that are known to interfere with contact lens wear (at the discretion of the investigator). This may include, but not be limited to entropion, ectropion, extrusions, chalazia, recurrent styes, glaucoma, history of recurrent corneal erosions, or corneal distortion.
5. Is using any topical ocular medications other than lubricating eye drops.
6. Known to have any infectious disease (e.g., hepatitis, tuberculosis) or a contagious immunosuppressive disease.
7. Have any systemic disease, autoimmune disease, or use of medication, which may interfere with contact lens wear (at the discretion of the investigator). This may include, but not be limited to, hyperthyroidism, recurrent herpes simplex/zoster, Sjogren's syndromes, xerophthalmia, acne rosacea, Stevens-Johnson syndromes.
8. Had a diagnosis of a condition known to affect ocular prescription or ocular surface or tear film e.g., rheumatoid arthritis, diabetes.
9. Had a change within the previous 3 months to the dosage of a systemic medication known to affect ocular prescription or ocular surface or tear film (e.g., steroids) that in the opinion of the investigator may affect a study outcome variable.
10. Has undergone cataract or refractive error surgery (e.g., radial keratotomy, PRK, LASIK, etc.), or has any planned (during the study) major surgery (e.g., hip replacement), or any planned ocular surgery (e.g., cataract or refractive error surgery).
11. Is a current rigid contact lens wearer, or is wearing contact lenses on extended wear basis, or has a history of extended wear in the past 6 months.
12. Has worn soft MF CLs in the past 2 years or is a habitual wearer of monovision CLs.
13. Has a constant unilateral strabismus at both far and near distances, or has anisometropia >2 D between both eyes, or has amblyopia.

14. Has a known sensitivity to the diagnostic pharmaceuticals to be used in the study (Refresh Plus[®] rewetting drop solution, or Sodium Fluorescein).
15. Has any Grade 3.0 or greater slit lamp findings (e.g., edema, corneal neovascularization, corneal staining, tarsal abnormalities, conjunctival injection) on the biomicroscopy classification scale, any previous history or signs of a contact lens-related corneal inflammatory event (e.g., past peripheral ulcer or round peripheral scar), or any other ocular abnormality that may contraindicate contact lens wear (at the discretion of the investigator).

3.4. Enrollment Strategy

All Subjects need to be in the presbyopic age group ie. ≥ 40 years old and with a minimum add of +0.75 D. There are no sex or race requirements.

All eligible Subjects will have no experience with soft multifocal lenses (MF CLs) for >2 years. The study population includes previous MF CL wearers, Single vision CL wearers and Subjects who are neophyte to CL wear. Current MF CL wearers and current monovision wearers are not eligible.

The study will include myopes only, with reading ADDs from +0.75 up to and including +1.75 DS.

4. STUDY DESIGN AND RATIONALE

4.1. Description of Study Design

This will be a prospective, single group, single-arm, and bilateral dispensing study. There will be no randomization and no masking in this non-controlled single-arm study. There also will be no wash out period. Subjects will be assigned to a single study lens type to be worn bilaterally in daily wear, and daily disposable modality, for at least 6 hours per day every day for approximately 12 weeks.

There will 6 visits in this study:

Visit 1: screening and baseline; eligibility confirmation, Quest questionnaire, pre-fit interview

Visit 2: baseline; personality test, study lens fitting

Visit 3: 1-week; CL power optimization

Visit 4: 2-week assessments with study CLs

Visit 5: 6-week assessments with study CLs

Visit 6: 12-week assessments with study CLs, post-fit interview

4.2. Study Design Rationale

This study was designed based on its exploratory nature. The single-arm design is used to explore differences in personality and qualitative interview variations as well as differences in refraction and anatomical measurements between successful and unsuccessful Subjects with study soft multifocal lenses.

4.3. Enrollment Target and Study Duration

- Up to approximately 75 Subjects will be screened, with a target of dispensing product to up to 50 subjects who may complete the study. Subjects will be recruited using CORE records and advertising approved by the University of Waterloo (UW) Office of Research Ethics (ORE).
- Point of enrollment in this study will be execution of informed consent.
- There will be a total of 6 study visits including the study screening visit during which consent, eligibility confirmation, interview and evaluation assessments will be conducted.
- The study will last approximately 9 months and include a 6 month enrollment period.
- This will be a single site study. Study visits will be conducted at Centre for Ocular Research & Education (CORE), University of Waterloo, Ontario.

5. TEST ARTICLE ALLOCATION AND MASKING

5.1. Test Article Allocation

There will be no randomization in this single arm study as there will be no controls, and only one test article is used.

5.2. Masking

Not applicable. There will be no masking in this study.

Subjects who are discontinued will not be replaced.

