Visit 1: Baseline			
Step	Procedure	Details	
1.8	Entrance Distance VA (spectacles) if applicable	
Record distance logMAR high contrast VA with the participant’s spectacles (if applicable): OD, OS, OU.
 
Note: The acuity will be recorded to the nearest letter OD, OS, and OU.
	
1.9	Ocular Symptoms	Subjects will respond to a verbal open-ended symptoms questionnaire.	
1.10	Quest-Quant Questionnaire	The subject will respond to the Quest-Quant Questionnaire.	
1.11	PRO (CLUE) Questionnaire (if applicable)	If Subjects are habitual contact lens wearers they will complete the PRO (CLUE) Contact Lens performance questionnaires.	
1.12	Auto-refraction & Keratometry	Record auto refraction and Keratometry results.	
1.13	Subjective Sphero-Cylindrical Refraction	
Conduct balanced subjective Best Sphero-cylindrical Refraction.
 
Record the refraction and distance logMAR visual acuity to the nearest letter.
 
Note: Best distance monocular visual acuity with sphero-cylindrical refraction must be at least +0.20 logMAR and binocular visual acuity of at least +0.10 logMAR with refraction for the subject to enroll in the study.
	
1.14	Near Add Determination	The near reading addition will be determined using the binocular crossed cylinder technique at 40 cm followed by optimization in a trial frame in step 1.20 below.	
1.15	Ocular Dominance	Determine ocular dominance	

1.16	ADD Refinement	Place the BCC result in the trial frame and refine the near prescription with trial lenses (or flippers) under binocular conditions.	
1.17	Near Visual Acuity	Measure Near logMAR at 40cm with near prescription in a trial frame. Record the near visual acuity OD, OS and OU.	
1.18	Unilateral Cover Test	Record presence/absence of strabismus in each eye (OD, OS) at distance with the Sph-cyl Refraction in Trial Frame. Then record presence/absence of strabismus in each eye (OD, OS) at near (40 cm) with the Sph-cyl Refraction and Near Add in Trial Frame.	
1.19	Biomicroscopy	Non-dilated Slit Lamp Biomicroscopy will be performed. If the clearance of the fluorescein needs to be expedited, preservative-free rewetting drops or saline may be instilled.	

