F.2	Investigator Recommendation	Investigator recommendation, if applicable (study CLs suitable/not suitable to prescribe, plus investigator reasons where not suitable is indicated) Proceed with final evaluation	
F.3	Distance Subjective Sphero-cylindrical Refraction	Perform an optimal monocular/binocular distance best sphero-cylindrical refraction and record the visual acuity (OD, OS, OU) to the nearest letter (this is referred to as the best corrected visual acuity, BCVA).	
F.4	Subject Disposition	Indicate the participant completed the study successfully or not. For subjects who discontinue, indicate the reason.	
F.5	PRO (CLUE & MRD) Questionnaires	Subjects will complete the PRO (CLUE and MRD) contact lens performance questionnaires.	

Final Evaluation			
Step	Procedure	Details	
	(Discontinued Subjects Only)		
F.6	Biomicroscopy (Discontinued Subjects if not completed during the visit)	Non-dilated Slit Lamp Biomicroscopy will be performed. If the clearance of the fluorescein needs to be expedited, preservative-free rewetting drops or saline may be instilled.	

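### An unmasked investigator judgement without stated criteria is part of the primary outcome, and no readable text keeps the recommending investigator from the Quest answers or class that the outcome is tested against

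*Combined protocol and SAP*

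**What the plan says.** Section 4.1 states: "There will be no randomization and no masking in this non-controlled single-arm study". Section 5.2, under the heading on test article allocation and masking, adds: "Not applicable. There will be no masking in this study".

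The success definition in Section 2.2 joins three conditions. The subject completes all required visits; "Investigator would recommend the study CLs, AND"; and the subject rates both overall vision and overall comfort on the MRD as good or better. Anyone else is classed as likely to be unsuccessful.

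The middle condition is recorded at step F.2 of the Final Evaluation (Section 7.2): "Investigator recommendation, if applicable (study CLs suitable/not suitable to prescribe". Reasons are asked for only when the answer is unfavourable. Step F.2 follows directly after the post-fit interview, F.1.

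The predictor is collected at Visit 1, step 1.10: "The subject will respond to the Quest-Quant Questionnaire". Section 4.3 says: "This will be a single site study".

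Section 2.3 names the one Quest class (discontented and driven) in which at least 75% are expected to succeed. Section 14.5 puts Quest class in the primary model as the fixed effect and concludes superiority if the lower 95% limit for that class exceeds 75%.

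**The concern.** The study asks whether a baseline classification predicts a later outcome. One component of that outcome is a person's opinion, and the protocol that person works from names the class expected to do well. If the person also knows a subject's class, or can guess it from the Quest answers, borderline recommendations can drift towards the hypothesis.

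Masking the lens has no meaning in a one-lens study. Masking the assessor to the predictor is a separate matter that needs no comparator, and the blanket no-masking statements leave it uncovered. Two things are at stake: the 75% conclusion for the named class, and the association between class and success that is the primary objective in Section 2.1.

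**Working it through.** **Step 1: is the recommendation a live part of the outcome?** Section 14.2 puts all analysis on the per-protocol population, and Section 14.3 limits that population to subjects who completed all visits. Completion is therefore constant in the analysis set. Success can vary only through F.2 and the two MRD ratings. Investigator approval is also a dispensing criterion at Visits 2 to 5 (steps 2.23, 3.22, 4.18 and 5.13), so the investigator's judgement also affects who completes.

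**Step 2: is it separated from the predictor?**

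| Question | What the readable text gives |
|---|---|
| Criteria for F.2 | None; only "study CLs suitable/not suitable to prescribe, plus investigator reasons where not suitable is indicated" |
| Who scores Quest, and when | Not stated |
| Whether the site is shown the class | Not stated |
| Whether the site is kept from answers or class | Not stated; masking excluded in general terms (4.1, 5.2, 5.3) |
| Investigator contact with recorded data | Investigator reviews and signs the eCRFs (15.1); whether Quest sits on an eCRF page is not stated |
| Quest content (Appendix A) | Not readable in the public document |

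Access to the answers is thus possible. Access to the class is neither documented nor excluded.

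**Step 3: which way can F.2 move the outcome?** The conditions are joined by AND. A favourable recommendation can rescue only a subject who completed, rated both MRD items good or better, and would otherwise have been judged unsuitable. An unfavourable one can turn any success into a failure. The scope is therefore narrower upwards than downwards.

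**Step 4: boundary illustration.** The plan gives no power calculation (14.2) and no class size, so there is no planned figure to reproduce. I assume class sizes n from 15 to 50 and use the exact (Clopper-Pearson) limit as a binomial stand-in for the covariate-adjusted mixed-model interval of Section 14.5. For x successes, the lower limit is the 0.025 quantile of Beta(x, n − x + 1). For example, 19/20 uses Beta(19, 2), giving 0.751, and 18/20 uses Beta(18, 3), giving 0.683.

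| Assumed n | Fewest successes that pass | Lower limit | One fewer | Lower limit |
|---|---|---|---|---|
| 15 | 15 | 78.2% | 14 | 68.1% |
| 20 | 19 | 75.1% | 18 | 68.3% |
| 25 | 24 | 79.6% | 23 | 74.0% |
| 30 | 28 | 77.9% | 27 | 73.5% |
| 40 | 36 | 76.3% | 35 | 73.2% |
| 50 | 44 | 75.7% | 43 | 73.3% |

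At the boundary, one subject decides the conclusion. That is true of any threshold rule on a binary outcome, masked or not. The table shows why a single discretionary judgement could matter; it does not estimate how often one would be swayed.

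**The case against.** The strongest reply is that knowledge of the class is conjecture. No readable step has the site score or classify Quest. Step 1.10 only has the subject answer it, whereas step 2.4 has the BIG5 score recorded. The class appears only in the objectives, endpoints, hypotheses and the analysis, which the sponsor runs (14.1). Scoring rules may sit in the unreadable Appendix A, and a single site does not mean a single person. All of this stands. A reader might infer that the recommending investigator knows who is discontented and driven, or that the result will be biased in favour of that class. The documents support neither inference.

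Second, Section 5 concerns the test article, where not applicable is correct. This also stands: the sentence in 5.2 is not wrong for its subject, and the gap is an omission about the assessor.

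Third, withholding Quest is only a partial remedy. Table 4 describes Quest-Quant as covering lens experience and expectations. The pre-fit interview (1.6) and post-fit interview (F.1) cover success criteria and the factors behind success or failure, so the investigator hears overlapping information anyway. This stands too, and is the reason for a sensitivity analysis alongside withholding.

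Fourth, the study is exploratory and unpowered (4.2, 14.2). That lowers the stakes but does not remove them, since Section 14.4 sets a 5% type I error rate and Section 14.5 a formal superiority rule.

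**Conclusion.** The point holds as an uncontrolled risk of bias. A required component of the primary outcome is an unmasked judgement without stated criteria, made at the site where the predictor was collected, under a protocol that names the class expected to succeed. Nothing readable separates the two.

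The size of any bias cannot be estimated from the documents. The figures above show only that, in a class of 15 to 50 subjects, one changed outcome at the boundary reverses the conclusion. They rest on assumed class sizes and a simple binomial interval. The upward route is limited to subjects who fail on the recommendation alone, and how many there would be is unknown.

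**What to change.** In Section 5.2, keep not applicable for lens masking and add that:

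- Quest is self-completed by the subject;
- Quest responses and any derived class are withheld from whoever makes the F.2 recommendation until F.2 is recorded and locked for that subject;
- the sponsor derives the class only after F.2 is recorded for all subjects.

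In Section 15.1, defer Investigator review and signature of any Quest eCRF page until after F.2, so that the restriction does not conflict with the sign-off duty.

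In Section 14.5, add a sensitivity analysis of the primary endpoint with success defined by completion and the two MRD items, without the recommendation. In the per-protocol set this reduces to the two MRD items. It addresses the overlapping information from the interviews, which withholding Quest cannot remove.

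The cost is a few sentences, an EDC view restriction if Quest is captured there, later sign-off of one form, and one extra analysis. No subjects, visits or procedures are added.

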
Study Design
	
This is a prospective, single-arm, and bilateral dispensing study.
 
There will a total of 6 visits:
 
Visit 1 (Screening and Baseline-day 0): consent, eligibility confirmation, pre-fit interview, and evaluation assessments
 
Visit 2 (Baseline & dispensing-Day 0): personality test, evaluation assessments, study lens fitting, CL insertion and removal training (non-CL wearers, up to 1 additional training appointments are permitted), subjective responses to CL performance, dispensing of CL
 
Visit 3 (1-week follow-up, lens power optimization-Day 7±3 from Visit 2): CL power optimization, lens fit assessment, evaluation assessments
 
Visit 4 (2-week follow-up- Day 7±3 from Visit 3): lens fit assessment, evaluation assessments, subjective responses to CL performance
 
Visit 5 (6-week follow-up Day 28±6 from Visit 2-): lens fit assessment, evaluation assessments, subjective responses to CL performance
 
Visit 6 (12-week follow-up Day 42±6 from Visit 2-): Post-fit interview, lens fit assessment, evaluation assessments, subjective responses to CL performance

	
Study exit: Investigator recommendation, if applicable (study CLs suitable/not suitable to prescribe, plus investigator reasons where not suitable is indicated), exit procedures. See the flow chart at the end of the synopsis table for the schematic of the study visits and procedures of main observations (Figure 1).

Sample Size	
The target is to dispense lenses to 50 presbyopic Subjects who had no experience with soft multifocal contact lens wear for >2 years; total sample size 50. Enrollment is potentially likely to be up to approximately 75 to account for screen failures.

Study Duration	
The study is anticipated to have a duration of approximately 9 months in total, with enrollment lasting approximately 6 months.

Anticipated Study Population	
All eligible Subjects will have no experience with soft multifocal contact lenses (MF CLs) for >2 years. The study population includes previous MF CL wearers, single vision CL wearers and subjects who are neophyte to CL wear; The target is to include myopes only, with a maximum reading addition of +1.75 DS.
 
There are no sex or race requirements. All subjects need to be in the presbyopic age group ie, ≥ 40 years old and with a minimum add of +0.75 D.
 
Current MF CL wearers and current monovision wearers are not eligible.

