8.2. Withdrawal/Discontinuation from the Study

A participant will be withdrawn from the study for any of the following reasons:

- Participant death during the study period
- Participant withdrawal of consent

- Participant not compliant to protocol (*not compliant with or not able to follow study procedures, or study procedures/interviews /assessments could not be conducted*)
- Participant lost to follow-up
- Participant no longer meets eligibility criteria (e.g. the participant becomes pregnant)
- Participant develops significant or serious adverse event during the study visit (e.g. a heart attack)
- Subjects presenting with a Corneal Infiltrative Event (CIE), or an eye infection
- Subject develops significant or serious adverse events causing discontinuation of study lens wear (missing more than half of the required days of lens wear in-between visits will lead to discontinuation, e.g. wearing the lens for only 1 day instead of the minimum of 4 days between visits 2 and 3)
- Investigator's clinical judgment regarding the participant safety reasons (that it is in the best interest of the participant to stop the study visit)
- Participant missed *two consecutive* study visits
- Participant not compliant with study lens wear schedule
- Participant not successfully dispensed due to lack of efficacy and safety including poor vision, poor comfort or unacceptable fit

For discontinued Subjects, the Investigator will:

- not complete the scheduled visit procedures
- Complete the Final Evaluation, indicating the reason that the participant was discontinued from the study
- Record the spherocylindrical refraction with best corrected distance visual acuity if applicable (i.e. if this was already measured during the same day) otherwise perform a spherocylindrical refraction and record the exit distance visual acuity.
- Collect used test article(s) (worn or brought to the visit) from the participant and discard them, unless otherwise stated in Section 7.2
- Collect all unused test article(s) from the participant

An additional participant may be enrolled if a participant discontinues from the study prematurely.

In cases where a participant is lost to follow-up, every possible effort must be made to contact the participant and determine the reason for discontinuation/withdrawal. The measures taken to follow up must be documented including two written attempts and a certified letter (or equivalent) as the final attempt.

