14.2. Sample Size Justification

This is an exploratory study to generate initial data for assessing a computational vision model. As such, the sample size was not determined based on any power analysis with regard to the primary endpoint. The collected data will be used to design future studies, if necessary.

The planned sample size (75 to enroll and 50 to complete) was selected to enroll different categories of myopic presbyopes including previous MF CL wearers, Single vision CL wearers and Subjects who are neophyte to CL wear. Efforts will be made to enroll subjects in all three categories without specific targets to be achieved.

All analysis will be conducted on the per-protocol population defined in section 14.3.

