14.3. Analysis Populations

Safety Population:

All Subjects who were administered any test article excluding Subjects who drop out prior to administering any test article. At least one observation should be recorded.

Per-Protocol Population:

All Subjects who have successfully completed all visits and did not substantially deviate from the protocol as determined by the trial cohort review committee prior to database hard lock (Per-Protocol Population). Justification of excluding Subjects with protocol deviations in the per-protocol population set will be documented in a memo to file.

Intent-to-Treat (ITT) Population:

All Subjects regardless of actual treatment and subsequent withdrawal from study or deviation from protocol. At least one observation should be recorded.

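### Sections 5.2 and 8.2 conflict on replacing discontinued subjects and the target of 50 has two meanings, so the analysed number is not fixed; the upward bias in the success rate comes from the completers-only analysis under either rule

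*Combined protocol and SAP*

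**What the plan says.** **Replacement.** Section 5.2, under Masking: "Subjects who are discontinued will not be replaced". Section 8.2, after the list of withdrawal reasons and the steps for discontinued subjects: "An additional participant may be enrolled if a participant discontinues from the study prematurely". Nothing says which governs.

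**Target.** Synopsis, Sample Size: "The target is to dispense lenses to 50 presbyopic Subjects". Section 4.3 also speaks of dispensing to up to 50, who may complete. Section 14.2 instead gives "The planned sample size (75 to enroll and 50 to complete", and says that no power analysis underlies it.

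**Outcome.** In section 2.2, success has three joint conditions, the first being "Completed all required study visits, AND". The unsuccessful group is everyone else: "Not meeting the definition of successful".

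**Analysis set.** Section 14.2: "All analysis will be conducted on the per-protocol population defined in section 14.3". Section 14.3 defines that population as "All Subjects who have successfully completed all visits and did not substantially deviate from the protocol".

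**Decision rule.** Section 14.5 concludes superiority if the lower 95% limit for the success proportion exceeds 75% in the class that the Quest questionnaire labels discontented and driven.

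**The concern.** The site has two enrolment rules and two readings of its target. No replacement fits a target of 50 dispensed; replacement fits a target of 50 completing. Staff cannot tell from the text when to stop enrolling, and the choice would be made in an unmasked study.

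The conflict matters more than usual because discontinuation settles the outcome. It is not the only route to failure (a negative investigator recommendation or a vision or comfort rating below good also suffices), but it is sufficient. At Visits 4 and 5, unacceptable distance or near vision leads to discontinuation (steps 4.5 and 5.5), so some dropouts are the very failures that the study sets out to characterise. How they enter the denominator bears directly on a proportion that is tested against 75%.

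**Working it through.** The plan has no power calculation to reproduce. The documents give no expected dropout rate (15% appears in section 14.9 only as the trigger for a sensitivity analysis) and no success rate among completers. Both are assumed here.

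**Inputs.** N = 50 dispensed; d = dropout after dispensing, 5% to 30%; q = success among completers, 80% or 90%. Replacements are taken to behave like the subjects they follow.

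**Formulas.**
- All dispensed, dropouts counted as unsuccessful: expected rate = (1 − d)q.
- Completers only: expected rate = q.
- Gap between the two sets: q − (1 − d)q = dq.

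None of these contains the number replaced. Replacement changes only the counts: without it about 50(1 − d) subjects complete; replacing until 50 complete needs about 50/(1 − d) dispensed.

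**Example: d = 15%, q = 90%.** (1 − 0.15) × 0.90 = 76.5%. In whole subjects, with exact (Clopper-Pearson) lower 95% limits:

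| Set | No replacement | Replace until 50 complete |
|---|---|---|
| All dispensed | 38/50 = 76% (61.8%) | 45/59 = 76% (63.4%) |
| Completers only | 38/42 = 90% (77.4%) or 38/43 = 88% (74.9%) | 45/50 = 90% (78.2%) |

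The first set has 50 × 0.85 = 42.5 expected completers, hence the two entries. Reading across a row, the rate barely moves. Reading down a column, it rises from about 76% to about 90%.

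**Range of the gap, dq.**

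| d | q = 80% | q = 90% |
|---|---|---|
| 5% | 76.0% vs 80% (4.0 points) | 85.5% vs 90% (4.5 points) |
| 15% | 68.0% vs 80% (12.0 points) | 76.5% vs 90% (13.5 points) |
| 30% | 56.0% vs 80% (24.0 points) | 63.0% vs 90% (27.0 points) |

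**Simulation check (400,000 runs; d from 10% to 30%).** With every dispensed subject kept, replacement moves the mean rate by about 0.1 to 0.4 points. Among completers it moves it by 0. At d = 20%, q = 90%, all dispensed: 72.0% without replacement, 72.2% after one round, 72.3% when replacing until 50 complete.

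**What replacement does change.** At d = 20% about 40 complete without replacement and 50 with it. At an observed 90%, the exact lower limit is 76.3% for 36/40 and 78.2% for 45/50. If the true rate is 90%, the chance that the exact lower limit exceeds 75% is 63% at n = 40 (36 successes needed) and 77% at n = 50 (44 needed).

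**Limit of the illustration.** The primary rule applies to one Quest class and uses a model-based interval, so these n are upper bounds. In an assumed class of 20, 18/20 = 90% has an exact lower limit of 68.3%.

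**The case against.** **A stronger reading.** A reader might infer that replacing dropouts would itself raise the success rate, because each replacement swaps a known failure for a new chance of success. The documents do not support this. Section 8.2 allows an additional participant; it does not provide for removing the discontinued one. Under section 14.3 every non-completer leaves the analysed set, replaced or not. Setting 38/50 against 45/50 changes the analysis set as well as the replacement rule; like for like, the rate stays where it was. Only deleting the dropout and counting the replacement in its place would raise it (at d = 20%, q = 90%, from 72.0% to 86.4% after one round), and no section says to do that.

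**The wording may be reconcilable.** Section 8.2 is permissive, so a site that never replaces breaks neither rule. It might also be meant for losses before dispensing, since enrolment is at consent (section 4.3) and section 7.2 calls ineligible subjects discontinued. The first point stands, but it does not tell a site whether replacement is allowed. The second is possible but unstated, and the reasons listed above the sentence include events after dispensing.

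**The study is exploratory and unpowered.** This is true and limits the consequences. Section 14.5 still sets a formal superiority rule against 75%, so the denominator has to be defined.

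**Missing data are addressed.** Section 14.9 adds multiple imputation as a sensitivity analysis if dropout exceeds 15%. That leaves the primary set unchanged, and for a subject who discontinued the outcome is not missing: section 2.2 already makes it unsuccessful.

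**Conclusion.** The conflict between sections 5.2 and 8.2 is real, and so is the split meaning of 50. Together they leave the number enrolled and analysed open. The effect of replacement is on precision, not on the expected rate: in the 20% dropout example it moves the lower limit at an observed 90% from 76.3% to 78.2%.

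The upward bias comes from analysing only completers when non-completion is failure by definition, and it is the same under either replacement rule. Its expected size is dq: 13.5 points at 15% dropout and 90% success among completers, and 4.0 to 27.0 points over the ranges tried. These rates are assumptions. The figures also treat all subjects as one group, whereas the test concerns the discontented-and-driven class, whose size is not stated. Crossing the 75% threshold is therefore shown as possible, not as expected, in the actual test.

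**What to change.** 1. Reconcile sections 5.2 and 8.2 into one rule, for example by keeping 5.2 and deleting the sentence in 8.2. If 8.2 is meant only for losses before dispensing, say so there.
2. State in the Synopsis and in sections 4.3 and 14.2 whether 50 means dispensed or completing.
3. Define the primary denominator as all dispensed subjects in the relevant Quest class. Count every one who discontinues, replaced or not, as unsuccessful. Amend the per-protocol-only sentence in 14.2 to match; the completers-only result can stay as a supporting analysis.
4. Report the number discontinued and, if any were replaced, the number replaced.

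Deleting the sentence in 8.2 alone would remove the conflict but leave the bias. The cost is a few sentences of amendment and no new data collection. The reported success rate will be lower and, without replacement, there will be somewhat fewer completers for the supporting analysis.
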